## **2.7. Anticipated findings and use of the data**

The findings from this project may result in a new standard counseling for PFPT that includes viewing of the educational video.

## **2.8. Subject compensation**

There is no subject compensation.

#### **4. Appendix**

##### **4.1. Standard care handout**

The Role of Physical Therapy in the Treatment of Pelvic Floor Dysfunction:

Physical therapists are trained to evaluate and treat dysfunctions in the joints, muscles, nerves and scar. Physical therapists specifically trained in the area of pelvic health can identify the possible musculoskeletal causes of pelvic pain, bladder and bowel difficulties and develop a treatment plan specific to the individual suffering from this difficulties.

What to expect at your first physical therapy appointment:

Your first visit will include an initial evaluation in a comfortable, private room by a therapist who has undergone advanced education and training in the evaluation and treatment of pelvic muscle dysfunction. The therapist will obtain a detailed history of your health, pain and activity limitations. She will also ask you about any bowel, bladder and sexual difficulties as these are in part controlled by the pelvic muscles. The therapist will then take a look at your posture, mobility of your spine and hips and strength and flexibility of pelvic girdle muscles. She will examine any scar tissue and trigger points in the muscles of your pelvic region.

The therapist will also specifically examine the pelvic floor muscles. Your pelvic floor consists of a group of muscles that attach behind the pubic bone in the front to the tail bone in the back. They are responsible for providing support to the pelvic joints and organs, relaxing to allow the passage of urine, stool and gas and contracting to prevent the loss of urine, stool and gas as appropriate. In order to best examine these muscles you will be asked to undress from the waist down and be covered with a sheet. The therapist will use a lubricated, gloved finger to identify painful muscles around and in your vagina or rectum then instruct you to contract and relax these muscles in order to determine how the muscles are functioning. Care is taken to make you as comfortable as possible with the exam.

Your therapist will discuss the evaluation results with you and provide you with education regarding your specific condition and the expectation of therapy. She will

answer all of your questions and will work with you to establish a treatment plan based on the results of the evaluation and your goals for therapy.

PAC can schedule for any of the locations and the phone number is [contact].

#### **4.3. Patient information collected (in clinic)**

Circle one:      Control      Intervention (video)

Age \_\_\_\_\_      Vaginal Parity \_\_\_\_\_      BMI \_\_\_\_\_

Insurance type:      Private      Government sponsored      Combined      Other

Race      Caucasian      Black      Asian      Eastern European      Hispanic      Other

Urogynecologic diagnoses (circle):      SUI      UUI      MUI      Urgency-frequency Syndrome

Weak pelvic floor      Defecatory dysfunction      POP      Myofascial pain      Other

Stage of Prolapse      0      1      2      3      4      Not Assessed

#### 4.4 Patient questionnaire

Do you have any further questions? No/Yes \_\_\_\_\_

1) After your visit today, how **well informed** do you feel about the role of pelvic floor physical therapy in treating pelvic floor symptoms?

### No change

## Very Informed

2) How do you rate the **ease of understanding** of information about pelvic floor physical therapy?

### Very difficult

Very easy

3) How do you rate the **amount of information** about pelvic floor physical therapy that was presented to you?

Not enough information

## Too much information

#### **4.5 Patient information collected (from EMR < nine months later)**

**Time to first PFPT visit from day of referral:** \_\_\_\_\_ days

**Physician who referred:**      [name]      [name]      [name]      [name]

**Number of recommended visits:** \_\_\_\_\_

**Number of completed visits:** \_\_\_\_\_

**Discharged from PFPT practice (circle):** yes      no

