### **1.3. Study Objectives and Hypotheses**

Objective: To determine the impact on PFPT compliance in patients who view an educational compared to standard counseling

Hypothesis: Compared to patients receiving standard counseling, those who receive both the standard counseling and educational video intervention will

- 1) Be more likely to complete at least half of their recommended PT visits
- 2) Be more likely to initiate PFPT
- 3) Will have a shorter time to initiation of PFPT
- 4) Be more likely to discharge from PFPT
- 5) Will have greater improvement in urogenital distress following PFPT

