#### **1.4. Summary of Study Design**

**Study Design:** Randomized controlled trial

**Population:** Clinic-based patients seen at the Loyola University Medical Center Urogynecology outpatient clinic who have been prescribed PFPT as a treatment for their condition and agree to such therapy.

**Control group:** Will read standard PFPT handout (see Appendix 4.1)

**Intervention group:** Will read standard PFPT handout plus watch education video (see Appendix 4.2)

**Study Length:** At least three months after the initial PFPT referral for each patient, medical record review will be performed to record therapy attendance, including date of first visit, number of visits recommended by the therapist, number of completed visits, and whether the patient was discharged from PFPT.

**Power-calculation:** One goal of the proposed study is to test the null hypothesis that the rate of women attending at least half of their required PT visits is identical in the two populations: Those assigned to handout only and those assigned to handout and video intervention. With proposed sample sizes of 96 assigned to handout only and 96 assigned to handout and video intervention, the study will have power of 80% to yield a statistically significant result.

This computation assumes that the difference in proportions of compliance is 20% (specifically, 70% versus 50% compliance for the intervention and control groups, respectively). It also assumes that the criterion for significance (alpha) will be set at 0.05 and that the test will be 2-tailed, meaning an effect in either direction will be interpreted.

This effect was selected as the smallest effect that would be important to detect, in the sense that any smaller effect would not be of clinical or substantive significance. It is also assumed that this effect size is reasonable, in the sense that an effect of this magnitude may be anticipated in this research.

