## **2.6. Statistical analysis**

Binary logistic regression will be used to compare the odds of PFPT initiation, PFPT discharge, completion of half of the recommended visits, and having any further questions after counseling between those assigned to the enhanced versus standard counseling groups. In these models, expected frequencies will be monitored and exact logistic regression models will be used when these values are sparse. We will also

stratify the comparison of PFPT initiation by participants' primary language. Because few patients will have Spanish as their primary language, we will make an *a-priori* decision to use an exact binary logistic regression model to compare the two treatment groups among Spanish speaking participants. Subsequently, a Breslow-day test may be used to compare the stratified English and Spanish speaking odds ratios for homogeneity.

A binary logistic regression model will also be used to estimate the odds of being discharged from PFPT as a function of the number of completed visits, and a Kaplan-Meier curve will be used to estimate the probability of not attending a PFPT visit following date of referral for those in the experimental and control cohorts. Using this approach, elapsed time will be measured in days from referral date to date of first visit for those who attended PFPT. Individuals who never attended PFPT will be censored at the last date they were known to be absent from therapy.

For each patient, the change in UDI-6 will be calculated by subtracting the post-treatment score from her pre-treatment score, and an independent samples *t*-test will be used to compare this change score between those assigned to the experimental group versus control group. In this model, normality and influential outliers will be assessed using QQ plots and box plots, respectively. A non-parametric Wilcoxon rank-sum test may be used if the data violate parametric assumptions. Finally, though a Kaplan-Meier method is primarily used to compare days from date of referral to date of first visit between the experimental and control groups, a Wilcoxon rank-sum test will also be used to make this comparison as a sensitivity analysis among those who attend PFPT. All analyses will be completed using SAS version 9.4 (Cary, NC).

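### Hypothesis 4 counts discharge as a benefit, but form 4.5 records it only as yes or no, so completed therapy and any closure after drop-out cannot be told apart

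*Combined protocol and SAP*

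**What the plan says.** Hypothesis 4 in section 1.3 states that women shown the video will "Be more likely to discharge from PFPT". Discharge is therefore a favourable outcome. Section 1.4 (Study Length) has the chart reviewer record "whether the patient was discharged from PFPT", and Appendix 4.5 provides one item to circle yes or no: "Discharged from PFPT practice (circle".

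Section 2.6 uses that item twice. Binary logistic regression will "compare the odds of PFPT initiation, PFPT discharge, completion of half of the recommended visits" between arms, and a second logistic model will "estimate the odds of being discharged from PFPT as a function of the number of completed visits".

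The same form holds "Number of recommended visits" and "Number of completed visits". Neither enters the definition of the discharge outcome. No section defines discharge, lists reasons for it, or ties it to finishing therapy. Section 1.4 places the chart review "At least three months after the initial PFPT referral for each patient", and the heading of Appendix 4.5 puts it at less than nine months.

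**The concern.** The item's label is discharge from the practice. On its face that covers a woman who finished therapy or met her goals, and also a woman whose episode was closed because she stopped coming. Both would be circled yes, and both would count in favour of hypothesis 4.

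Any closure of the second kind is a failure scored as a success. It would distort the comparison of arms whenever the arms differ in the share of women who start and then drop out. It would also add discharges at low visit counts to the discharge-by-visits model. Once abstraction is finished, the reason could be recovered only by reopening charts.

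The answer no is mixed as well: it covers women still in therapy at the review, women who dropped out without being closed, and women who never started.

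**Working it through.** **The plan's own figure.** Section 1.4 gives 80% power with 96 per arm for 70% v 50%, two-sided alpha 0.05. This is for attending at least half of visits, not for discharge. The two-proportion z test, power = Φ((d − 1.96·SE0)/SE1) with SE0 pooled and SE1 unpooled, gives 81.2%, which reproduces it. The plan states no power for discharge.

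**Size of the group at risk.** Section 1.1 reports that 66% of referred women attended at least once, and that 73% of those attended at least half of their visits.
- Reached half: 0.66 x 0.73 = 48.2% of those referred.
- Started but did not reach half: 0.66 x 0.27 = 17.8%, or about 17 of 96 per arm at past rates.

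**Effect of closing drop-outs as discharged.** Let a be the share of women who start but drop out whose chart is closed and circled yes, taken as equal in both arms. For each arm:

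observed yes = (discharged with therapy completed) + a x (started, then dropped out).

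The documents give no value for a, so it runs from 0 to 1. The video arm's rates are also assumed. Power is for 96 per arm.

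*Scenario A: the video raises initiation and retention.* Control: 66% start, 48% reach half, 18% drop out. Video: 80% start, 68% reach half, 12% drop out. Of those reaching half, 70% are assumed discharged on completion. Control = 0.48 x 0.70 + 0.18a; video = 0.68 x 0.70 + 0.12a.

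| a | Control | Video | Difference (points) | Power |
|---|---|---|---|---|
| 0 | 33.6% | 47.6% | 14 | 51% |
| 0.5 | 42.6% | 53.6% | 11 | 33% |
| 1 | 51.6% | 59.6% | 8 | 20% |

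*Scenario B: the video raises initiation, with the documented 73% retention in both arms.* Initiation is 66% v 80%, with the same 70% discharge rate. Drop-outs are 0.66 x 0.27 = 17.8% v 0.80 x 0.27 = 21.6%, so more in the video arm. Control = 0.66 x 0.73 x 0.70 + 0.178a; video = 0.80 x 0.73 x 0.70 + 0.216a.

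| a | Control | Video | Difference (points) | Power |
|---|---|---|---|---|
| 0 | 33.7% | 40.9% | 7.2 | 17% |
| 0.5 | 42.6% | 51.7% | 9.0 | 24% |
| 1 | 51.5% | 62.5% | 10.9 | 33% |

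*Scenario C: the video raises initiation only, with no effect on completion.* Initiation is 66% v 80%, and discharge with therapy completed is 48% in both arms. Drop-outs are 0.66 − 0.48 = 18% v 0.80 − 0.48 = 32%. The true difference is zero.

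| a | Control | Video | False difference (points) | Chance of significance favouring video |
|---|---|---|---|---|
| 0 | 48.0% | 48.0% | 0 | 2.5% |
| 0.25 | 52.5% | 56.0% | 3.5 | 7% |
| 0.5 | 57.0% | 64.0% | 7 | 17% |
| 1 | 66.0% | 80.0% | 14 | 59% |

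In every scenario the difference moves by a x (video drop-out share − control drop-out share). That term is negative in A and positive in B and C, so the sign of the bias depends on which arm has more women who start and then leave.

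**The case against.** The strongest reply is that the premise is not in the documents. Nothing says that the therapy practice closes charts for non-attendance, or that it would call this discharge. If it does not, a = 0 and there is no bias. This stands: the missing definition is a fact of the text, while its consequence is conditional.

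Second, recommended and completed visits are on the same form, so a yes with few visits can be spotted without new data, and the discharge-by-visits model would show such cases as discharges at low counts. This stands in part. No such check is planned, and visit counts cannot separate an early discharge with goals met from closure after drop-out.

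Third, discharge is not the outcome behind the sample size. That is correct and limits the weight of the point.

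A reader might also infer that the error is conservative: control should have more drop-outs, so miscoding could only hide a true benefit. The documents do not support that. It needs better retention among starters in the video arm (in scenario A, 68/80 = 85% against 73%), and no section gives such a figure. Section 2 has the video shown at the referral visit, before any therapy, so an effect mainly on initiation is at least as plausible. The difference can then widen, or appear where none exists.

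**Conclusion.** The point holds as a gap in outcome definition. With a yes/no item and no reason, the data cannot show whether a discharge in hypothesis 4 is completed therapy or a closed chart. The group at risk is about 18% of referred women at past rates.

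The size of any bias is unknown because the closure share is unknown. Over the full range from 0 to 100%, the arm difference moves from 14 to 8 points, from 7 to 11, or from 0 to 14, depending on assumed effects on initiation and retention. These are illustrations and not forecasts. They support bias in either direction, and they do not support a claim that closures for non-attendance do occur.

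This is a cheap improvement to a secondary hypothesis. Hypothesis 1 and the sample size are unaffected.

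**What to change.** - On form 4.5, replace the yes/no item with discharge status: therapy completed or goals met; closed for non-attendance; other or reason not documented; still in therapy; never started or not discharged.
- In section 2.6, define the outcome for hypothesis 4, and for the discharge-by-visits model, as discharge with therapy completed or goals met.
- Report women still in therapy at chart review separately by arm. Section 1.1 describes weekly sessions and up to fifteen visits, and the review may fall as early as three months, so some cannot yet have finished and should not be read as failures.
- Add a sensitivity analysis that scores discharges with an undocumented reason first as successes and then as failures.

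The cost is slightly more abstraction time in charts that are already being opened, and some notes will lack a clear reason. The sensitivity analysis shows how much those matter. The change affects data capture and analysis only, and it should be made before abstraction starts.
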